7.6.1.10. Pain-free

Pain free is defined as an NRS score of 0 or 1 with no rescue medication use prior to that assessment.

7.6.2. Methods of Analysis

7.6.2.1. Primary Efficacy Analysis

The primary efficacy analyses will be conducted for both the primary and secondary efficacy analysis sets. Results from the primary efficacy analysis set will be primary efficacy result; the analyses based on the secondary efficacy analysis set are a sensitivity analysis.

The primary efficacy variable is the AUC of NRS scores from first postsurgery assessment (0.25 hours) through 48 hours [AUC(0.25-48)] using the wWOCF to adjust for rescue medication use and multiple imputation method to account for missing data described in Section 7.1.1.1.1.

Tests for the treatment effect of EXPAREL versus placebo will be based on the following null hypothesis (H_0) and two-sided alternative hypothesis (H_a):

$H_0: \mu_s = \mu_p$ versus $H_a: \mu_s \neq \mu_p$

where μ_s and μ_p are the mean of AUC(0.25-48) for EXPAREL and the mean of AUC(0.25-48) for placebo, respectively. A two-sided test will be performed at 5% level of significance. The treatment effect of EXPAREL will be considered significantly better than that of placebo if the null hypothesis of no difference is rejected and a difference in mean of AUC(0.25-48) in favor of EXPAREL (mean for EXPAREL < mean for placebo) is observed.

For the primary efficacy variable of AUC(0.25-48), EXPAREL will be compared to placebo using analysis of variance (ANOVA) with treatment and site as main effects. Based on the model, the least squares (LS) means, LS mean difference between the two treatment groups, 95% confidence interval (CI) for the LS mean difference between the two treatment groups, and p-value will be reported.

Descriptive statistics of the primary efficacy variable will also be shown by site but no statistical analyses will be performed by site.

In addition, an ANOVA model with main effects of treatment and site and the treatment by site interaction will be reported to assess the interaction on the primary efficacy analysis. Additional analyses may be performed if the interaction effect is significant (p-value <0.05).

Sensitivity Analyses

Mixed Model Repeated Measures

A mixed model repeated measures analysis will be performed using only the data imputed using wWOCF but not imputing any missing values outside of the rescue medication windows. The MMRM model will have fixed effects for treatment and time. The initial model will be fit with the treatment-by-time interaction. If this interaction is not significant (p-value > 0.05) the final model will include the main effects only. If the interaction is significant (p-value ≤ 0.05) the interaction will be investigated to determine if it is qualitative or quantitative. If the interaction is quantitative, the final model will include the interaction term. If the interaction is qualitative, additional analyses may be required. The treatment effect at 48 hours will be estimated from the final model.

Tipping Point

A tipping point analysis will be performed using similar imputation technique as the primary AUC calculations (see section [7.1.1.1.1](#)) but adding shift values to the imputation until the primary analysis results change direction (SAS pseudo-code below).

```
PROC MI DATA=OUTDATA_STEPB OUT=OUTDATA_TIP;
  BY _IMPUTATION_;
  CLASS TREATMENT;
  MONOTONE REG(T1 = TREATMENT / DETAILS);
  MONOTONE REG(T2 = TREATMENT T1 / DETAILS);
  ...
  MONOTONE REG(T(n-1) = TREATMENT T1 T2 T3 ... T(n-2) / DETAILS);

  MNAR ADJUST(T1 / SHIFT=Q ADJUSTOBS=(TREATMENT='EXPAREL'));
  MNAR ADJUST(T2 / SHIFT=Q ADJUSTOBS=(TREATMENT='EXPAREL'));
  ...
  MNAR ADJUST(T(n-1) / SHIFT=Q ADJUSTOBS=(TREATMENT='EXPAREL'));
  MNAR ADJUST(Tn / SHIFT=Q ADJUSTOBS=(TREATMENT='EXPAREL'));

  VAR TREATMENT T1 T2 T3 ... Tn
RUN;
```

where Q is the value to shift the results.

If the result from the primary efficacy analysis is statistically significant, the above code will be run iteratively for integer values of Q from 1 to 10 analyzing each step of the way until the result “tips” from statistically significant to not statistically significant. If the primary efficacy analysis result is not statistically significant, the above code will be run iteratively for integer values from -1 to -10 until the result “tips” from not clinically significant to clinically significant. The value of Q that results in the change in significance will be reported along with the analysis results.

Original Imputation Method

The AUC of NRS scores from first postsurgery assessment (0.25 hours) through 48 hours [AUC_{0(0.25-48)}] will also be derived using the methodology used in previous submission, wWOCF + LOCF as described in Section [7.1.1.1.2](#). AUC_{0(0.25-48)} will be analyzed for the primary and secondary analysis sets using an analysis of variance with fixed effect of treatment reporting the the least squares (LS) means, LS mean difference between the two treatment groups, 95% confidence interval (CI) for the LS mean difference between the two treatment groups, and p-value along with descriptive statistics.

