Perform dental nerve block with lidocaine 2% with epinephrine 1:100,000			X ²																							
Administer study drug; record start and stop time			X																							
Conduct NRS pain intensity assessment ⁴				X	X	X	X	X	X	X	X							X			X		X			
Record times and amounts of opioid rescue medication administered ⁵				←																	→					
Subject satisfaction with postsurgical pain control													X				X			X		X		X		
Complete PoSSe scale questionnaire																					X		X		X	
Collect scheduled PK blood sample			X ²	X	X	X	X	X		X	X	X	X	X	X	X	X	X	X	X	X	X	X	X		
Document any unscheduled phone calls or office visits related to pain after hospital discharge																							X	X	X	
Phone call																										X
Record concomitant medications			←	→																						→
Record AEs (starting at signing of ICF) ⁶			←	→																						→

Abbreviations: AE = adverse event; ICF = informed consent form; NRS = numeric rating scale; PK = pharmacokinetic; PoSSe = postoperative symptom severity.

* Postsurgical efficacy assessments will be conducted at the timepoints specified *after the beginning of study drug administration*. At timepoints when multiple assessments coincide, the NRS pain intensity assessment will be conducted first, if applicable.

¹ Or on Day 1 prior to surgery.

² Prior to surgery.

³ Vital signs (heart rate and blood pressure) will be measured after subject has rested in a supine position.

⁴ NRS pain intensity scores also will be recorded immediately prior to each administration of rescue pain medication through 96 hours.

⁵ Subjects should only receive opioid rescue medication (oral oxycodone 5-10 mg) upon request for breakthrough pain, as needed (maximum of every 4 hours). During the 96-hour observation period, no other analgesic agents, including nonsteroidal anti-inflammatory drugs (NSAIDs), are allowed. After 96 hours, the analgesic regimen may be adjusted.

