9.2. Discussion of Study Design

EXPAREL is approved for infiltration into a surgical site. This multicenter, randomized, double-blind, placebo-controlled study is designed to evaluate the safety, efficacy, and pharmacokinetics of local administration of EXPAREL for prolonged postsurgical analgesia in subjects undergoing third molar extraction. The double blind study design is intended to avoid potential bias resulting from subject or Investigator knowledge of the assigned treatment.

Third molar extraction is a frequently performed surgical procedure that causes considerable postsurgical pain, particularly following removal of impacted lower mandibular third molars. Standard postoperative analgesia following third molar extraction often includes combination opioid analgesics. In this study, all subjects will receive PO oxycodone, as needed, to control breakthrough postsurgical pain.

Neurological and cardiac assessments will be conducted to rule out bupivacaine toxicity related to high plasma exposure.

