10. STUDY POPULATION

10.1. Inclusion Criteria

Subjects eligible for study entry must meet all of the following criteria:

1. Male or female, ≥ 18 years of age at screening.
2. Scheduled to undergo bilateral third molar extractions (i.e., extraction of all four third molars) under local anesthesia. At least one lower mandibular third molar must involve full or partial bony impaction confirmed by visual or radiological evidence.
3. American Society of Anesthesiology (ASA) physical status 1, 2, or 3.
4. Female subjects must be either surgically sterile, using a medically acceptable method of birth control, or at least 2-years postmenopausal and must have a documented negative pregnancy test result during screening and on Day 1 prior to surgery.
5. Able to provide informed consent, adhere to the study visit schedule, and complete all study assessments.

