11.3.2. Randomization Procedures

Once a subject is identified as being qualified for the study per the eligibility criteria (see [Section 10.1](#) and [Section 10.2](#)), and is at the study site for surgery, the research pharmacist or designee will obtain a randomization assignment. The subject will be considered randomized into the study once the study treatment assignment is received.

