11.5. Blinding

11.5.1. Blinding Procedures

EXPAREL and placebo are visually distinguishable; therefore, to maintain the double-blind study design, only unblinded study personnel who are NOT involved with protocol-specific, postsurgical assessments may prepare the study drug. Staff members conducting study-specific, postsurgical assessments and the subjects will remain blinded to the assigned treatment throughout the study. If a subject experiences a serious AE (SAE), Pacira will not automatically unblind the subject's treatment, unless it is necessary to manage treatment of the SAE. Expedited SAEs will be unblinded by Pacira for regulatory reporting purposes.

At each site, only the individual(s) who are designated to receive unblinded randomization assignments will be responsible for preparing study drug.

Site surveys suggest that study sites will vary in their standard (and feasible) procedures for preparing sterile study drug in a blinded fashion. Therefore, each site will be responsible for providing their written blinding procedures for study drug preparation and transportation. This documentation (e.g., site-specific blinding plan) will be made available to Pacira for review before the site enrolls a subject into the study. The site-specific blinding plan will outline the study treatment blinding process that will be followed at the site throughout the study. Assignment of blinded and unblinded responsibilities regarding the preparation of study drug should take into account that **EXPAREL may not be held in a syringe for more than 4 hours after preparation for administration.**

Once the study drug is prepared in syringes as a sterile preparation, it will be placed under a sterile drape on a sterile tray for use when needed. The individuals preparing study drug will not be allowed to perform any of the study assessments or reveal the assigned study treatment to any other members of the study team at any time. Syringes containing study drug will need to be gently inverted several times to re-suspend any settling of the study drug that may have occurred prior to administration. Should administration of the study drug involve extension tubing or a butterfly needle, then any visible tubing needs to be covered with aluminum foil to maintain the blind.

The administration of study drug will be recorded using the minimal amount of information necessary to avoid unblinding staff who will be participating in blinded procedures.

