13.3. Baseline Procedures (Day 1)

- Confirm eligibility.
- Update relevant medical history.
- Perform urine pregnancy test for women of childbearing potential before study drug administration.
- Perform urine drug screen.
- Measure vital signs (heart rate and blood pressure) after subject has rested in a supine position.
- Perform neurological assessment (see [Appendix 4](#)).
- Conduct 12-lead ECG.
- Collect baseline (pre-dose) blood sample for PK analysis prior to study drug administration.
- Record changes to concomitant medications since screening.
- Record AEs.
- Randomize subject and prepare study drug.

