12. MULTIPLE IMPUTATION EXAMPLE PROGRAM CODE

** Note: INPUT_DATA is the dataset that contains the NRS data with the wWOOF imputation performed for the rescue pain scores **;

** Step 1 use Markov-Chain Monte-Carlo (MCMC) method to create a monotonic missing pattern **;

** Note the value for the random seed should be fixed so that the results are reproducible **;

PROC MI DATA=INPUT_DATA SEED=M NIMPUTE=1000 OUT=OUTPUT_STEP1;

 BY TREATMENT;

 MCMC IMPUTE=MONOTONE NBITER=2000 NITER=1000;

 VAR TIME_POINT_LIST;

RUN;

** Step 2 – use regression on output dataset from Step 1 to impute missing values **;

** T_i is the variable containing the pain score from time i **;

PROC MI DATA=OUTPUT_STEP1 OUT=OUTPUT_STEP2;

 BY _IMPUTATION_;

 CLASS TREATMENT;

 MONOTONE REG(T_1 = TREATMENT / DETAILS);

 MONOTONE REG(T_2 = TREATMENT T_1 / DETAILS);

...

 MONOTONE REG($T_{(n-1)}$ = TREATMENT $T_1 T_2 T_3 \dots T_{(n-2)}$ / DETAILS);

 MONOTONE REG(T_n = TREATMENT $T_1 T_2 T_3 \dots T_{(n-1)}$ / DETAILS);

 VAR TREATMENT $T_1 T_2 T_3 \dots T_n$

RUN;

** Dataset OUTPUT_STEP2 is as an ADaM dataset, include in DEFINE.XML and transfers **;

** Step 3 derive endpoint using appropriate techniques by variable _imputation_ **;

** Endpoints are: AUC(0.25-48), AUC(0.25-24), AUC(0.25-72), SPI(0.25-24), SPI(0.25-48), **;

** SPI(0.25-72) and integrated rank assessment at 24, 48 and 72 hours **;

** Step 4 get summary statistics **;

** Summary step 4a get the mean of all imputation endpoint values for each subject **;

PROC SUMMARY DATA=OUTPUT_STEP2;

 BY TREATMENT USUBJID;

 VAR ENDPOINT_VARIABLE;

 OUTPUT OUT=SUMMARYSTATSA MEAN=ENDPOINTMEAN;

RUN;

** Dataset SUMMARYSTATSA is as an ADaM dataset, include in DEFINE.XML and transfers **;

** SUMMARYSTATSA also source for a data listing **;

** Summary step 4b use subject imputation means to derive summary statistics **;

PROC SUMMARY DATA=SUMMARYSTATSA;

 BY TREATMENT;

[figure not shown]
 VAR ENDPOINTMEAN;

 OUTPUT OUT=SUMMARYSTATSB N=N MEAN=MEAN STDDEV=STDDEV MEDIAN=MEDIAN
 MIN=MIN MAX=MAX;

RUN;

```
*** Step 5 analyze imputations **;  
ODS OUTPUT ESTIMATES=MIXEDSTATSA;  
PROC MIXED DATA= OUTPUT_STEP2 METHOD=TYPE3;  
    BY _IMPUTATION_;  
    CLASS TREATMENT SITE;  
    MODEL ENDPOINT_VARIABLE = TREATMENT SITE;  
    ESTIMATE 'EXPAREL - PLACEBO' TREATMENT 1 -1;  
RUN;  
  
ODS OUTPUT PARAMETERESTIMATES=MIXEDSTATSB;  
PROC MIANALYZE DATA= MIXEDSTATSA ALPHA=0.05 THETA0=0;  
    MODELEFFECTS ESTIMATE;  
    STDERR STDERR;  

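### A cheap improvement, not an error: the primary ANOVA adjusts for treatment and site only, although a per-tooth impaction grade is already recorded

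*SAP*

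**What the plan says.** SAP 7.6.2.1 sets the primary model for AUC(0.25-48): "EXPAREL will be compared to placebo using analysis of variance (ANOVA) with treatment and site as main effects". The code in SAP section 12 agrees: "MODEL ENDPOINT_VARIABLE = TREATMENT SITE". SAP 7.6.2.2 analyses AUC(0.25-24) and AUC(0.25-72) the same way. Protocol 15.6.3.1 had treatment alone; the SAP added site.

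On impaction, Protocol 9.2 says that third molar extraction "causes considerable postsurgical pain, particularly following removal of impacted lower mandibular third molars". Protocol 10.1 makes it an entry condition: "At least one lower mandibular third molar must involve full or partial bony impaction confirmed by visual or radiological evidence". SAP Listing 16.2-4 (Surgery) carries a grade for each of teeth 1, 16, 17 and 32: fully bony, partially bony, soft tissue or erupted. Section 3 of the SAP addendum scores these grades 10, 1, 0 and 0 and tabulates them by treatment, jaw, site and surgeon. It also refits the ANOVA with surgeon in place of site. No visible text puts impaction into an efficacy model.

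**The concern.** The plan names a likely driver of pain, grades it in every subject and checks its balance between arms, but leaves it out of the one place where it could reduce variance. A tabulation shows a chance imbalance in impaction; it does not remove it from the estimated treatment difference.

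What is at stake is precision. If impaction predicts AUC within site and arm, the planned interval is somewhat wider than it need be.

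**Working it through.** **Inputs.**
- Two-sided alpha 0.05 (SAP 7.6.2.1).
- Difference 66 with SD 100, or 86 with SD 130; 50 per group for 90% power (Protocol 15.3, SAP section 8).
- The decision set is the Amendment 2 subjects (SAP section 6), with at least 50 treated per arm (Protocol 15.3). Allocation under Amendment 2 is 2:1 (SAP section 4), so 50 on placebo goes with 100 on EXPAREL.
- Three sites, 100, 200 and 300 (addendum table shells), so site uses 2 df.
- Partial R-squared of the score, within site and arm: not in the documents. Assumed 0, 0.02, 0.05, 0.10 or 0.20.

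**Step 1: the plan's own figure.** Two-group t-test, 50 per arm, df 98. Noncentrality is 66 / (100 × √(2/50)) = 66/20 = 3.30, giving power 90.4%. For 86 with SD 130 it is 86/26 = 3.31, giving 90.6%. The stated 90% reproduces.

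**Step 2: planned model.** With treatment and 3 sites, df = N − 4. At 50/50 the SE is 20 and power is 90.4%. At 100/50 the SE is 100 × √(1/100 + 1/50) = 17.32, noncentrality is 66/17.32 = 3.81, and power is 96.6%.

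**Step 3: one added linear covariate.** df = N − 5. The variance is multiplied by (1 − R²) and by the expected chance-imbalance factor 1 + 1/(N − 4 − 2). That factor is 1 + 1/94 = 1.0106 at 50/50 and 1 + 1/144 = 1.0069 at 100/50. Two examples at 50/50, difference 66:
- R² = 0: SE = 20 × √1.0106 = 20.11; 66/20.11 = 3.28; power 90.1%.
- R² = 0.10: SE = 20 × √(0.90 × 1.0106) = 19.07; 66/19.07 = 3.46; power 92.9%.

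| Case | Planned | R²=0 | 0.02 | 0.05 | 0.10 | 0.20 |
|---|---|---|---|---|---|---|
| Power %, 100/50, 66, SD 100 | 96.6 | 96.5 | 96.8 | 97.2 | 97.8 | 98.8 |
| Power %, 100/50, 86, SD 130 | 96.7 | 96.6 | 96.9 | 97.3 | 97.9 | 98.8 |
| Power %, 50/50, 66, SD 100 | 90.4 | 90.1 | 90.7 | 91.5 | 92.9 | 95.3 |
| Power %, 100/50, 50, SD 100 | 81.8 | 81.5 | 82.3 | 83.5 | 85.4 | 89.2 |
| 95% CI half-width, 100/50, SD 100 | 34.2 | 34.4 | 34.0 | 33.5 | 32.6 | 30.7 |

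A difference of 50 is not a design value; it lies inside the 20 to 103 range that Protocol 15.3 reports.

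**Step 4: break-even and worst case.** The gain starts where (1 − R²) times the factor falls below 1: R² above about 1 − 1/1.0106 = 1.1% at 50/50, or 1 − 1/1.0069 = 0.7% at 100/50. At R² = 0 the loss is 0.1 point at 100/50 and 0.3 point at 50/50 for difference 66. The largest loss found is 0.46 point (50/50, difference 50: 69.7% to 69.2%). Simulation with the 0-to-3 grades below and assumed grade shares (30,000 trials per case) agrees: 90.5% to 90.2% at 50/50, difference 66, R² = 0. Type I error at R² = 0.10 was 5.0% unadjusted and 5.1% adjusted.

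**Step 5: coding.** Score erupted 0, soft tissue 1, partial bony 2, full bony 3, and sum teeth 17 and 32. The seven eligible grade pairs then total 2 to 6. The addendum's coding gives the same pairs 1, 2, 10, 11 or 20 and merges soft tissue with erupted, which suits a tabulation but not a linear term. Entering five levels as categories (4 df) would cost about 1.3 points at 50/50 (90.4% to 89.2%), so the single linear term matters.

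**The case against.** The case for leaving the model alone is strong on several points.

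- **No defect.** Treatment plus site is valid and matches its code. This stands.
- **The gain is assumed.** The support is one qualitative sentence in Protocol 9.2. Eligibility already demands bony impaction of a lower third molar, so much of the contrast is removed by design, and nothing says that pain rises from partial to full bony. Site may also absorb part of any effect. This stands, which is why R² is taken within site and arm and shown as a range starting at zero. At 100/50 and the design differences the gain is at most 2.2 points, and that needs R² = 0.20.
- **The source is uncertain.** The dental examination is done at screening ("Or on Day 1 prior to surgery", per the Table 1 footnote), but Listing 16.2-18 shows only visual or radiological confirmation and an X-ray date. Subjects confirmed visually may have no film. This stands; the usable grade is the one in the Surgery listing. Its grader and timing are not stated, subjects are randomised before surgery (Protocol 11.3.2 and 13.3), and "EXPAREL and placebo are visually distinguishable". Against that, study drug is given at the end of surgery (Protocol 13.4), in a blinded manner (Protocol 11.1), so the graded anatomy precedes it. Confirmation is needed, not new data.
- **Timing.** The addendum refers to existing data, with named sites and recorded lidocaine doses. Unblinding status is not stated. If unblinding has occurred, only sensitivity use remains.
- **Scoring.** Equal spacing and ignoring the upper teeth are choices the documents do not make. A poor choice lowers the gain; it does not bias the comparison.

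**Conclusion.** A worthwhile low-cost improvement with a small and uncertain benefit. It rests on three assumptions: the score has a partial R² above about 1%; three sites enter the model; the recorded grade is a blinded description of the tooth before study drug. No dropout was applied, and the effect of multiple imputation on degrees of freedom was ignored.

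A reader might infer that the primary analysis is biased, underpowered or loose on type I error. The documents do not support that: the model is valid and the stated power reproduces. A reader might also infer that adjustment is sure to help because the protocol calls impaction painful. No figure in the documents shows how much AUC variance impaction explains among eligible subjects. Nor can one say that the sponsor never planned such a model: the visible addendum points to its Section 2 for detail, and part of that section was not available, so a further change cannot be excluded.

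**What to change.** Before unblinding, amend SAP 7.6.2.1 and the section 12 code:

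1. Define the covariate: the sum over teeth 17 and 32 of erupted = 0, soft tissue = 1, partial bony = 2, full bony = 3, entered as one linear term.
2. Take it from the grade recorded for Listing 16.2-4, after documenting that it describes the tooth as found before study drug and was entered without knowledge of allocation. Resolve missing grades by query. No new X-ray reading is asked for.
3. Fit treatment + site + score for AUC(0.25-48), AUC(0.25-24) and AUC(0.25-72).
4. Add the score to the Step 1 variable list and each Step 2 regression of the imputation code.
5. Keep treatment + site as the supportive model.

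If item 2 cannot be confirmed, or unblinding has occurred, leave the primary model as planned and report the adjusted model only as a labelled sensitivity analysis.

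The cost is one degree of freedom, a few lines of text and code, one check on how the grade was recorded, and 0.1 to 0.5 point of power if impaction predicts nothing.

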15.3. Determination of Sample Size

In previous wound infiltrations studies in hemorrhoidectomy and bunionectomy, the difference between treatment groups in mean AUC from 0 to 48 hours or NRS pain intensity scores varied from 20 to 103. The standard deviations varied from 100 to 128. A sample size of 50 in each group will have 90% power to detect a difference in means of 66 assuming that the common standard deviation is 100 using a two group t-test with a 0.05 two-sided significance level. A sample size of 50 in each group will have 90% power to detect a difference in means of 86 assuming that the common standard deviation is 130 using a two group t-test with a 0.05 two-sided significance level.

However, the EXPAREL group will randomize approximately 100 subjects to lower the AE detection threshold for the safety database to 3%. The sample size for placebo was increased due to the additional collection of NRS pain intensity score immediately prior to all requests for rescue medication through 96 hours. The placebo sample size was increased to ensure that there are at least 50 subjects treated in both the EXPAREL and placebo under the current protocol amendment. It is expected that the sample size will be approximately 175 subjects resulting in a 2:1 ratio of EXPAREL to placebo subjects.

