4. STUDY OVERVIEW

This is a Phase 3, randomized, double-blind, placebo-controlled study in subjects scheduled to undergo elective bilateral third molar extraction (i.e., extraction of all four third molars) under local anesthesia. At least one lower mandibular third molar must involve full or partial bony impaction confirmed by visual or radiographic evidence.

Approximately 175 subjects (at least 100 in the EXPAREL group and 50 in the placebo group) are planned for enrollment. Subjects enrolled under Amendment 1 were randomized in a 1:1 ratio. Due to FDA feedback Amendment 2 changed the randomization ratio to 2:1 (EXPAREL: placebo), thus subjects enrolled under Amendment 2 will be randomized in a 2:1 ratio to receive local administration of a single dose of either EXPAREL (133 mg/10 mL) or placebo (normal saline, 10 mL).

The timing of all assessments is in the Time and Events Schedule of study procedures (Section 10) and further described in the protocol.

Screening

Subjects will be screened within 30 days prior to surgery. During the screening visit, subjects will be assessed for any past or present medical conditions that in the opinion of the Investigator would preclude them from study participation.

Day 1 (Day of Surgery)

On Day 1 prior to surgery, any AEs or changes in concomitant medications since screening will be recorded, vital signs will be measured, a urine drug screen will be conducted for all subjects, and a urine pregnancy test will be conducted for women of childbearing potential. A pre-dose PK sample will be collected from all subjects eligible for randomization. Randomized subjects will receive a dental nerve block with lidocaine 2% with epinephrine 1:100,000 before undergoing bilateral third molar extraction under local anesthesia

At the end of surgery, and at least 20 minutes after the lidocaine administration, a total of 10 mL of study drug will be infiltrated [4 mL (2 mL per side) into the maxilla and 6 mL (3 mL per side) into the mandible].

Subjects will be required to remain in the research facility for 96 hours after study drug administration.

Postsurgical Safety and Efficacy Assessments

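### The three AUC analyses fit one variance to both arms of a 2:1 primary set, so the standard error and 95% CI are modestly miscalibrated if the arm SDs differ.

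*SAP*

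**What the plan says.** SAP 7.6.2.1 sets the primary test: "EXPAREL will be compared to placebo using analysis of variance (ANOVA) with treatment and site as main effects". The hypothesis concerns means only, "where μ_s and μ_p are the mean of AUC(0.25-48) for EXPAREL and the mean of AUC(0.25-48) for placebo, respectively", and "A two-sided test will be performed at 5% level of significance". SAP Section 12, Step 5, programs the model as "PROC MIXED DATA= OUTPUT_STEP2 METHOD=TYPE3" with "MODEL ENDPOINT_VARIABLE = TREATMENT SITE". The code shown has no variance grouping by arm, no robust standard error and no degrees-of-freedom adjustment, so both arms share one residual variance. SAP 7.6.2.2 analyses AUC(0.25-24) and AUC(0.25-72) the same way; these are the first two steps of the fixed sequence in SAP 7.1.2.

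On allocation, SAP Section 4 says "Subjects enrolled under Amendment 1 were randomized in a 1:1 ratio" and then "Due to FDA feedback Amendment 2 changed the randomization ratio to 2:1 (EXPAREL: placebo"). SAP Section 6 bases the efficacy decision on Amendment 2 subjects alone, so the deciding set is 2:1 throughout.

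The sample-size text (Protocol 15.3, SAP Section 8) assumes 50 per group and a common SD. On earlier studies it says "The standard deviations varied from 100 to 128", without splitting that range by arm.

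**The concern.** With equal arms, the pooled and separate-variance standard errors of a difference in means coincide, so unequal SDs do almost no harm. At 2:1 that protection is lost, because the larger EXPAREL arm dominates the pooled variance. The allocation changed with Amendment 2, but the analysis kept a common variance.

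Unequal SDs are plausible for this endpoint. The NRS is bounded at 0 and 10, worst-score replacement applies only to subjects who take rescue medication, and a treated arm may mix responders and non-responders. These mechanisms do not all point the same way.

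At stake are the primary p-value and 95% CI, and the two AUC tests that follow. No listed sensitivity analysis covers the point. The MMRM does not state its covariance structure and estimates the effect at 48 hours, not the AUC. The tipping-point analysis shifts imputed values only. The wWOCF+LOCF analysis, the secondary-set analysis and the addendum's surgeon model are again ANOVAs with no variance by arm.

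**Working it through.** **The plan's own figure.** Two-group t-test, 50 per group, two-sided 0.05. Noncentrality is difference / (SD × √(2/50)): 66 / (100 × 0.2) = 3.30 gives 90.5% power, and 86 / (130 × 0.2) = 3.31 gives 90.6%. The stated 90% reproduces.

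**Inputs.** Alpha 0.05 two-sided (SAP 7.6.2.1). Arm sizes 100 and 50 (SAP Section 4, stated as minimums for the whole trial and assumed here for the primary set). They fit the total of about 175 if some 25 subjects, 12.5 per arm, entered under Amendment 1: (100 + 12.5) + (50 + 12.5) = 175. The protocol's 100:75 is shown as an alternative. Arm SDs are an assumption: 100 and 128, the ends of the stated range (ratio 1.28), with 100 and 115 as a milder case.

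**Formulas.**
- Common-variance SE = √[s²p (1/nE + 1/nP)], with s²p = [(nE−1)σ²E + (nP−1)σ²P] / (nE + nP − 2).
- True SE = √(σ²E/nE + σ²P/nP).

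In large samples the first becomes √(σ²E/nP + σ²P/nE): each arm's variance is divided by the other arm's size. With nE = nP the two agree; at 2:1 they do not.

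**Numbers for 100:50, EXPAREL SD 100, placebo SD 128.** s²p = (99 × 10,000 + 49 × 16,384) / 148 = 12,113.6. Common-variance SE = √(12,113.6 × 0.03) = 19.06. True SE = √(100 + 327.68) = 20.68. The ratio is 0.922.

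**Results** (400,000 simulated trials per case, normal complete data, no site effect):

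| Arms | SD EXPAREL / placebo | Common-variance SE | True SE | 95% CI coverage | Rejection rate, equal means |
|---|---|---|---|---|---|
| 100:50 | 100 / 100 | 17.32 | 17.32 | 95.0% | 0.050 |
| 100:50 | 100 / 128 | 19.06 | 20.68 | 92.9% | 0.071 |
| 100:50 | 128 / 100 | 20.69 | 19.07 | 96.7% | 0.033 |
| 100:50 | 100 / 115 | 18.22 | 19.09 | 93.8% | 0.062 |
| 100:50 | 115 / 100 | 19.10 | 18.23 | 96.0% | 0.040 |
| 100:75 | 100 / 128 | 17.24 | 17.85 | 94.2% | 0.058 |
| 100:75 | 128 / 100 | 17.85 | 17.24 | 95.7% | 0.043 |
| 75:75 | 100 / 128 | 18.76 | 18.76 | 95.0% | 0.050 |

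A separate run with a true difference of 66 (200,000 replicates) gave coverage of 93.0%, 96.6%, 93.9% and 96.0% for the four unequal-SD cases at 100:50; the small differences are simulation error.

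**With site in the model** (three sites, 40,000 simulations, SD ratio 1.28): rejection at equal means was 0.071 or 0.034 at 100:50, and 0.051 or 0.049 at 75:75.

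**With variances by arm at 100:50.** The Welch test rejected at 0.049 to 0.051 for every SD pair tried. With site in the model, HC2 standard errors gave 0.049 to 0.052 and HC3 0.046 to 0.049. With EXPAREL SD 128 and placebo SD 100, power for a difference of 66 was 90.4% with a common variance and 92.9% with separate variances. With equal SDs it was 96.6% and 96.5%.

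**When a decision would change.** With placebo SD 128, significance on the true SE needs a common-variance t of 1.976 × 20.68 / 19.06 = 2.14, that is p of about 0.034 on 148 degrees of freedom. So only results with p between about 0.034 and 0.050 would lose significance. At SD 115 the window starts at 1.976 × 19.09 / 18.22 = 2.07, p of about 0.040. At the design difference of 66, the ratio to the SE moves from 66 / 19.06 = 3.46 to 66 / 20.68 = 3.19, with the same conclusion.

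**The case against.** A reader might infer that the primary test runs at a 7% error rate. The documents do not support that. If EXPAREL does nothing, both arms have the same AUC distribution, hence equal SDs, and the common-variance test holds 5%. The 0.071 needs a drug that changes the spread of AUC while leaving its mean exactly equal. The SAP's null is worded on means alone, so that case lies within it, but it is a narrow one. What survives without that condition is CI coverage, which is affected whenever the SDs differ.

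A reader might also take 100 to 128 as the SDs of the two arms. The text describes variation across earlier hemorrhoidectomy and bunionectomy studies and gives nothing by arm, so 1.28 is an assumed ratio and the direction is unknown. In the conservative direction, power at the design difference is still 90.4%.

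Other points also stand. ANOVA was prespecified in Protocol 15.6.3.1 and matches the common-SD sizing. SDs by arm are printed in SAP Table 14.2-1.1.1, so a marked imbalance would be visible. The Amendment 2 arm sizes are not fixed in the documents, and at 100:75 the effect is smaller. The simulations used complete normal data and did not reproduce wWOCF, multiple imputation or Rubin pooling.

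These points limit the size of the concern but do not remove it. Imputation leaves the common-variance assumption of Step 5 in place, and a descriptive SD does not correct the reported interval.

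**Conclusion.** The point holds as a conditional, modest robustness weakness. It does not show that the primary test is invalid. In an all-2:1 set, the planned model gives a CI that is too narrow if placebo has the larger SD and too wide if EXPAREL does; a 1:1 set would have avoided this. The departure is about two points of coverage at the widest SD ratio the stated range allows, about one point at ratio 1.15, and under one point at 100:75. These sizes rest on assumed arm SDs, assumed primary-set sizes and normal complete data. A change of conclusion would need a borderline p-value. The change is worth making because the remedy costs almost nothing, and it applies equally to the 24-hour and 72-hour AUCs.

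**What to change.** Before unblinding, amend SAP 7.6.2.1, 7.6.2.2 and Section 12 Step 5 for the three AUC analyses:

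- Keep treatment and site, and estimate a separate residual variance for each arm. In the code, replace METHOD=TYPE3 with REML and add a REPEATED statement with GROUP=TREATMENT and DDFM=SATTERTHWAITE. An HC2 or HC3 robust standard error is an acceptable alternative.
- Carry the complete-data degrees of freedom into PROC MIANALYZE through EDF=. The code shown passes only the estimate and its standard error, so a Satterthwaite adjustment would otherwise be lost at pooling. State how one value is chosen when the degrees of freedom vary across imputations.
- Keep the common-variance ANOVA as a supporting analysis.

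The cost is a few code changes, more than one model statement, and about 0.1 point of power if the SDs are equal (96.5% against 96.6% at a difference of 66).
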